RESEARCH PROTOCOL

Study title: Safety and effectiveness of hyaluronic acid and sorbitol with overuse knee pain in sportsmen

Protocol Reference ethics committee number: CEI/0504/PI./2022

ClinicalTrials.gov: NCT05450458

DATE: 01/12/2023

ABSTRACT

INTRODUCTION

KNEE OVERUSE KNEE SYNDROME

ETIOLOGY

DIAGNOSIS

IMAGE DIAGNOSIS

CLASSIFICATIONS

OVERUSE KNEE SYNDROME TREATMENT

NON SURGICAL

ANTIINFLAMATORY NON STEROIDEAL TREATMENT

INFILTRATIONS

PHYSIOTHERAPY

HIALURONIC ACID TYPES:

HYALURONIC ACID PLUS SORBITOL

EVALUATION

RESEARCH QUESTION

PROTOCOL JUSTIFICATION

HYPOTHESES

HYPOTHESIS

NULL HYPOTHESIS

OBJECTIVES

MAIN OBJECTIVE

SPECIFIC OBJECTIVES

MATERIALS

STUDY DESIGN

SELECTION CRITERIA

INCLUSION CRITERIA

EXCLUSION CRITERIA

ELIMINATION CRITERIA

VARIABLES

POPULATION UNIVERSE

POPULATION SIZE

STUDY DESIGN

STATISTICAL ANALYSIS

ETHICAL IMPLICATION

ORGANIZATION

APPENDIX 1

APPENDIX 2

APPENDIX 3

REFERENCES

Abstract:

Introduction: The presence of overuse syndrome has been found with increasing frequency in patients who perform impact sports activities. Repetitive micro-trauma as a result of intense sport will cause the onset of joint degeneration that will generate pain, functional disability and in some cases limitation to continue carrying out sports activities.

Aims: the aims of this prospective and longitudinal intervention cohort study is to evaluate the safety and efficacy of hyaluronic acid plus sorbitol through clinical and functional analysis of sports patients undergoing overuse knee syndrome.

Patients and Methods:

According to the inclusion criteria, the participants who agree to part of the study will be enrolled, two dose of hyaluronic acid plus sorbitol will be applied in each knee, then strategies techniques for continue with sports activities. The KOOS and IKDC scores will be evaluated at 15 days 3 and 6 months. Once we obtain all data results a statistical analysis will be made.

Introduction:

It is increasingly common to find patients who refer knee pain after any kind of sports, overuse syndrome of the knee has been the most common cause. This entity can be conditioned by repetition microtrauma which are in direct relation with the repenting rise of the intensity, duration and volume in sports activity, and also we could find incorrect training techniques or also do not count with appropriate equipment during training.

Knee Overuse Syndrome

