To evaluate safety and efficacy of hyaluronic acid with sorbitol in athletes with overuse knee pain by comparing functional outcomes at short, medium and long term after treatment.

Specific Objectives

- To assess the safety and efficacy of hyaluronic acid with sorbitol in patients with sports-associated knee pain.
- To compare the clinical and functional results of patients with sport-associated knee pain after before and after treatment.

METHODS

Study Design

This research will be a cohort study, prospective and unidirectional direction.

Selection Criteria

- Patients with knee pain for more than 3 months
- Patients between 30 and 55 years old
- Patients without a history of previous knee joint surgery.
- Patients without chronic-degenerative diseases such as diabetes, hypertension, rheumatoid arthritis or other autoimmune diseases.
- Patients who perform impact social sports at least 3 times a week for more than 1 hour in the last 3 months prior to treatment.
- Patients without a history of allergies to non-steroidal anti-inflammatory drugs.
- Patients with no history of infection in or around the knee.

EXCLUSION CRITERIA

- Patients who cannot be categorized as social athletes.
- Patients with an associated sports injury that limits their sports practice.
- Patients who have a treatment associated with knee pain independent of that established in the study protocol.

ELIMITATION CRITERIA

- Patients who suffer from an injury or illness during the study that may limit their sports activity or who require an analgesic or anti-inflammatory treatment other than that established in the protocol.
- Patients who personally want to leave the study.
- Patients who did not have complete follow-up during the study.
- Patients who present an allergic or infectious reaction related to hyaluronic acid or prolotherapy or sepsis and antisepsis methods for infiltration.
- Patient with an allergic reaction to non-steroidal anti-inflammatory drugs.

VARIABLES

Variable	Operational Definition	Dimension	Variable type	Instrument	Indicator
Age	Time of life of any person	Without categories	Quantitative Discrete	Interview	Years
Gender	Biological and physiological characteristics that differentiate a man from a woman	Female Male	Qualitative Nominal	Interview	Gender
Body Mass Index	Score calculated by weight and height of a person.	Normal Overweight Obesity	Quantitative Discrete	Measuring tape Weighing machine	Weight in kg / Height in square meters

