Affected Knee	Anatomic Knee side	Left	Qualitative	Physical Exploration	Left

		Right	Nominal		Right
Athlete	Person who practice any type of sport	Social Amateur Professional	Qualitative Nominal	Interview	Have a sports activity for more than 3 months, 3 times a week over 60 minutes per session
Score KOOS	Scores that evaluate functional and osteoarthritis around the knee	Symptoms Joint Stiffness Pain Regular activities Sports activities Quality of life	Quantitative Discrete	Interview Physical Exam	Percentage 0-100%
Score IKDC	International Knee Documentation Committee	Symptoms Regular Activities Sports Activities	Quantitative Discrete	Interview Physical exam	Percentage 0-100%
Visco supplementation	Intraarticular joint injection of high weight molecular hyaluronic acid with sorbitol	Mono dose Multi dose	Qualitative Nominal	Hyaluronic acid 2ml plus sorbitol 2 dose per knee	Yes = Knee joint infiltration No= Did not apply
Training sports technique	Coaching for adequate techniques of certain sports	Manual technique Instrumented	Qualitative Nominal	Personalized coaching techniques	Achievement survey

	activities			Or Information brochure	
--	------------	--	--	----------------------------	--

Research Universe

General Population who does sports activities and have knee overuse syndrome between June of 2022 and October 2022.

Sample Size

It will be a non-probability sampling where will be chosen participants who meet selection criteria over the enrolling time which will be for 5 months. The lower limit will be 60 participants and the higher limit will be 120 participants.

Sample size formula: $n(\text{sample})$, z (confidence level), p (probability to occur the studied event), q (probability to didn't occur the studied event) and e (maximum accepted estimated error)

$$Z^2 * p*q$$

$$n = \frac{Z^2 * p*q}{e^2}$$

Study Design

Research enrolling and diffusion will be initiated after authorization of the ethics and investigation committee. All participants with knee pain related to sports will be accepted for a physical evaluation. All participants will be interviewed about physical activities, sports, injuries, and knee pain. Once they have been categorized as athletes with knee overuse pain syndrome and have met the selection criteria, then will be invited to the research. For this, the participants must be agreed and sign the informed consent Appendix 1 and 2.

Before treatment Group

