To participants who initiate the study research will be applied the KOOS and IKDC scores, the results will be recorder in the collection data sheet. Appendix 2. Participants will be explored by physical exam focus on knee pathology, and also an echography knee scan

looking for non-overuse pain injuries. Coaching for sports activities will be explained for each patient in order to improve its own training techniques adding stretching exercises for previous and after training.

After treatment Group

After KOOS and IKDC scores were recorded two doses of Hyaluronic Acid plus sorbitol will be applied. Technique: On the examination table, the patient will lie down at supine position and the area of the knees to be infiltrated will be discovered. Asepsis of the knee region will be performed using an iodine and alcohol solution, the remaining synovial fluid in the joint will be extracted with a 10cc syringe then 4 milliliters of 80 mg of hyaluronic acid plus 160 mg of sorbitol will be applied (Synolis VA Aptissen S. A.) at the sub quadriceps level with a 22G x 32mm sterile needle. At the end of the infiltration, the needle will be removed, and the injection site will be covered with a small sticky-band, which can be thrown away after 20 minutes. It will be recommended to not make any kind of sports activity following the next 72 hours and apply ice therapy 3 times per day for over 20 minutes. Scores recorded data will be made at 15 days, then at 3 and 6 months.

Once the enrolling phase of the trial is concluded, statistical analysis will be made with Excel Office software for Windows, IBM SPSS and Prism.

Statistical analysis

Recorded data of the functional scores will be evaluated before and after treatment, also at 15 days, 3 and 6 months after hyaluronic acid supplementation.

Data analysis will be made by means standard deviation for numeric variables, also t-test for parametric and Wilcoxon Mann Whitney for non-parametric variables, a standard error of 95% is allowed. Differences in time will be calculated and group compared by Anova test. Variable correlation and association measures with relative risk and attributable risk with Fisher's test will be made with a confidence interval of 95%.

Ethical Implications

This research project will be developed after approval of the ethics and research Institutional committee.

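### The methods text times the analysis to the end of a 5-month enrolment, before any 6-month score can exist, and the abstract gives an incompatible trigger

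*Combined protocol and SAP*

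**What the plan says.** All references are to the combined protocol and SAP.

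- **Trigger in the methods** (Study Design, After treatment Group, last sentence): "Once the enrolling phase of the trial is concluded, statistical analysis will be made". The rest of the sentence lists the software.
- **Trigger in the abstract** (Patients and Methods): "Once we obtain all data results a statistical analysis will be made".
- **Length of enrolment** (Sample Size): the sample is formed from "participants who meet selection criteria over the enrolling time which will be for 5 months", with 60 participants as the minimum and 120 as the maximum. Research Universe gives a matching calendar period, describing people who "have knee overuse syndrome between June of 2022 and October 2022".
- **Follow-up** (After treatment Group, immediately before the trigger): "Scores recorded data will be made at 15 days, then at 3 and 6 months". The abstract gives the same schedule.
- **What is analysed** (Statistical analysis): the functional scores before treatment and at each of the three visits after it, including 6 months. This section does not say when the analysis is done.

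No section describes an interim analysis, a data cut-off or a database lock.

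**The concern.** The two triggers refer to different times. At the end of enrolment the latest entrants have only just been treated. Having all the data means that the last entrant's 6-month visit is over. Because enrolment is shorter than follow-up, the gap between the two affects every participant's last visit, not just those of late entrants.

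If the methods sentence were followed as written, the 6-month comparison would have no data and the 3-month comparison would rest on the earlier entrants alone. If the sentence is read loosely, the plan has no firm cut-off, and the time of analysis is left open in an uncontrolled before-after study of patient-reported scores. A plan should settle this in advance.

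**Working it through.** The plan gives no figure for how many participants would have data at the time of analysis, so there is none to reproduce. The limits of 60 and 120 serve only as denominators. The sample size formula has no bearing on this point.

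**Inputs**

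- Length of enrolment: 5 months (Sample Size). The calendar check from Research Universe is 1 June to 31 October 2022, at most 152 days, and 152 / 30.4375 = 4.99 months.
- Visit times after treatment: 15 days (15 / 30.4375 = 0.49 months), 3 months and 6 months.
- Planned number: 60 to 120.

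**Step 1: the 6-month visit, with no accrual assumption.** The longest follow-up anyone can have when enrolment closes equals the length of enrolment. That is 5 months, and 5 < 6. The number with a 6-month score is therefore 0 of 60 and 0 of 120. On the calendar, a participant treated on 1 June 2022 is due for the 6-month visit about 1 December 2022, which is 31 days after 31 October. Treatment given later than enrolment would only lengthen the gap.

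**Step 2: the earlier visits, under an assumption.** Assume uniform accrual and treatment on the day of enrolment. The share that has reached visit time *t* when enrolment closes is max(0, (5 − *t*) / 5).

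| Visit | Calculation | Share | Of 60 | Of 120 |
|---|---|---|---|---|
| 15 days | (5 − 0.49) / 5 | about 90% | 54 | 108 |
| 3 months | (5 − 3) / 5 | 40% | 24 | 48 |
| 6 months | max(0, (5 − 6) / 5) | 0% | 0 | 0 |

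Faster early accrual would raise the first two rows and slower early accrual would lower them. The third row does not change.

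**Step 3: the abstract's trigger.** All data are in when the last entrant has passed 6 months, which is 5 + 6 = 11 months after enrolment opens. For enrolment closing on 31 October 2022 this is about the end of April 2023. Every retained participant could then have a 6-month score.

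The two triggers are therefore about 6 months apart, and only the later one allows the analysis that the Statistical analysis section describes.

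**The case against.** The strongest reply is that the intended timing is plain from the rest of the text. The trigger directly follows the visit schedule, and the section after it uses 6-month scores, which an analysis at the end of enrolment could not supply. The abstract waits for all the data. The trigger sentence is mainly a list of software, its opening can be read as an earliest time rather than a start date, and the enrolling phase may be a slip for the follow-up phase. Most of this stands, and it is why the point is minor. It does not remove the point: the only statement of timing in the methods is the wrong one, and reading it as an earliest time leaves no cut-off at all.

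A second reply is that the matter may be past. The document is dated 01/12/2023. If that means 1 December 2023, all 6-month visits from the stated window were already due. The date could also mean 12 January 2023, when many were not. This bears on the practical effect and does not correct the text.

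Three stronger readings are tempting, and the documents do not support them:

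- **That nobody could be analysed.** The elimination criteria remove "Patients who did not have complete follow-up during the study", and a reader might apply this at the end of enrolment. But a participant whose 6-month visit is not yet due has not failed follow-up, and nothing says the criterion is applied at that time.
- **That the type I error is inflated by two looks.** Each trigger produces one analysis, and no section plans both. For the 6-month comparison a look at the end of enrolment would contain no data, so there would be nothing to inflate. No primary time point is named to which an overall error rate could be attached.
- **That the abstract directly contradicts the methods.** It gives a later trigger that is incompatible with analysis at the end of enrolment. It does not deny the methods sentence, and the document sets no order of precedence between the two.

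**Conclusion.** The point holds as a minor inconsistency that is wrong as written. Under the methods trigger, 0 of 60 to 120 participants could have 6-month scores. This rests only on the stated 5-month enrolment and 6-month last visit. The figures of about 40% at 3 months and about 90% at 15 days also assume uniform accrual and treatment on the day of enrolment. The abstract and the statistical section make a drafting slip the likely explanation, so this is a correction of wording and not evidence that the 6-month analysis was meant to be skipped or that an early look was planned.

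**What to change.** Replace the trigger at the end of After treatment Group with a sentence such as: a single analysis will be carried out after the last enrolled participant has completed the 6-month visit, or has passed the window for it, and the database has been locked. The software list can follow unchanged. Use the same trigger in the abstract. The text gives no visit window, so state one for the 6-month visit.

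If an analysis has already been done, report the data cut-off that was used, so that readers can tell whether the 6-month results come from completed follow-up.

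The cost is a small text change and no new visits or data. The analysis waits about 6 months after the last enrolment, which the visit schedule already requires.

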Composition: Each 1 ml contains: hyaluronic acid 20 mg, Sorbitol 40 mg, phosphate buffered solution 1ml. Synolis VA contains a 2 ml siringe of viscoelastic solution.

Contraindications.

Synolis VA should not be used in:

- Patients known to be hypersensitive to hyaluronic acid or sorbitol.
- Pregnant lactating patients
- Minors
- Skin disease or infection at the level of the application site.

CLINICAL EVALUATION

The knee injury and Osteoarthritis Outcome Score (KOOS) is a new, well-designed, and simple self-administered instrument developed to assess short, and long-term symptoms and function in patients with knee injuries and osteoarthritis. It has good evidence of reliability, validity, and responsiveness in different populations with different pathologies, injury duration, ages, and activity levels. The KOOS scale has been shown to be very effective in Young and active patients; it is intended to be used in short and long-time intervals; to assess week-to-week changes induced by treatment (medication, surgery, physical therapy). All items were scored from 0 to 4, and each of the five scores was calculated as the sum of the included items; scores are then converted to a scale of 0-100, where zero represented extreme knee problems and 100 represented no knee injury, this can be represented as a percentage.

The INTERNATIONAL KNEE DOCUMENTATION COMMITTEE IKDC, is a patient-oriented score to qualify symptoms and functions related to the activity of daily living; evaluates knee injuries and categorizes them into subjective variables, symptoms, ranges of motion and ligamentous exploration, which is subcategorized into normal, almost normal, abnormal and severely abnormal, the objective of this scale is to provide the physician with information on patient satisfaction and their knee. Points on the *Subjective Knee Assessment Form* are calculated by adding the points for the individual items, and then transforming the points on a scale from 0 to 100. The transformed points are interpreted as a measure of the ability to function, with higher points representing higher levels of functioning and lower levels of symptoms. One hundred points are interpreted to mean that there is no limitation in activities of daily living or sports activities, and the absence of symptoms.

Justification and Statement of the Problem

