Currently there is a major influence to promote sport in the population, however, despite its great benefits, the development of early osteoarthritis secondary to micro-trauma due to overuse must be taken into consideration. In fact, the presence of early osteoarthritis following a prolonged or intense period of physical activity, or in those who practice impact sports regularly, is well described. Athletes who have initial stages of osteoarthritis require a treatment that improves their clinical symptoms and improves functional functions for as long as possible. Another objective of treatment is for their daily sports activities; sports activities; intraarticular HA injections are more effective in young patients, especially in the long term, while the results are less promising in athletes with advanced osteoarthritis. Reducing the viscoelasticity of synovial fluid, the transmission of mechanical force to the cartilage increases susceptibility to mechanical damage. Therefore the restoration of normal joint homeostasis is the reason for the administration of hyaluronic acid in the joints, in addition to seeking a physiological healing process and, if possible, complete; secondly, to shorten the recovery time, especially in athletes who are not going to limit their activity. The currently evidence that exists regarding the efficacy and safety of viscosupplementation in athletes is limited, hence the present investigation arises from the understanding that there are no protocols that demonstrate the benefits of knee joint infiltration using hyaluronic acid plus sorbitol in athlete patients, so in order to determine the safety and efficacy of this treatment, the following research question is proposed:

RESEARCH QUESTION

Is there a clinical and functional difference in the short and medium term in patients with knee pain due to overuse associated with sports treated by infiltration with hyaluronic acid with sorbitol?

Hypothesis

Athletes with sports-related overuse knee pain have Good clinical and functional results in the short and medium term through joint infiltration of hyaluronic acid with sorbitol.

Null Hypothesis

Athletes with knee pain due to sports-related overuse do not have Good clinical and functional results in the short and medium term through joint infiltration of hyaluronic acid with sorbitol.

Objectives

General Objective

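### No primary score, primary visit, multiplicity rule or usable significance level is set for 6 to 18 before-after tests of one undefined success hypothesis

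*Combined protocol and SAP*

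**What the plan says.** - **Scores and visits.** The abstract says: "The KOOS and IKDC scores will be evaluated at 15 days 3 and 6 months". The Statistical analysis section says: "Recorded data of the functional scores will be evaluated before and after treatment, also at 15 days, 3 and 6 months". Baseline scores are taken before the injection.
- **Tests.** The same section lists "t-test for parametric and Wilcoxon Mann Whitney for non-parametric variables", then an ANOVA for differences over time. It does not say whether the two-sample or paired form is meant, whether tests are one- or two-sided, or how the ANOVA relates to the visit tests.
- **Error level.** For these tests the only statement is "a standard error of 95% is allowed". A 95% level is used properly only in the next lines, on association measures: "Fisher's test will be made with a confidence interval of 95" per cent.
- **What KOOS is.** The Clinical evaluation section describes separate 0-100 scales ("each of the five scores was calculated as the sum of the included items") and defines no total. The Variables table enters KOOS as one variable with one percentage indicator and these dimensions: "Symptoms Joint Stiffness Pain Regular activities Sports activities Quality of life".
- **What is to be shown.** The Hypothesis is that athletes "have Good clinical and functional results in the short and medium term". Good is not tied to a score, a visit or a threshold. The general objective speaks of functional outcomes at short, medium and long term. No primary endpoint is named anywhere.

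**The concern.** Several scores are compared with baseline at three visits, and all of the results bear on one hypothesis. Nothing fixes in advance which result decides it. Someone reporting this study could choose the favourable score or visit after seeing the data and still be within the written plan. The significance level that should limit chance findings is not stated either, so even a single test has no defined threshold.

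At stake is how far a reported significant improvement can be trusted as more than chance. There is also a mismatch of question: the tests ask whether the mean change differs from zero, while the hypothesis asks whether results are good.

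**Working it through.** **The plan's own figures.** The plan states no alpha, power or family-wise error, so there is nothing to reproduce on error rates. Its one design figure is 60 to 120 participants, beside n = Z²pq/e². No values are given for Z, p or e, so it cannot be reproduced, and it points to no particular score or test.

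**Inputs from the documents.** Three follow-up visits. KOOS is either one score (Variables table) or five (Clinical evaluation). IKDC is one score. The table lists six KOOS dimensions because stiffness is shown separately, but Appendix 2 places the stiffness items under Symptoms, so five is used.

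**Assumptions.** Two-sided 5% per test, and no true change on any score. Correlation between tests is not in the documents, so independence and a common correlation of 0.7 are shown.

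**Number of visit tests, k.**
- KOOS as one score: (1 + 1) × 3 = 6
- KOOS as five scores: (5 + 1) × 3 = 18

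**Independent tests.**
- At least one significant result in either direction, 1 − 0.95^k: k = 6 gives 0.265; k = 18 gives 0.603.
- At least one significant improvement, 1 − 0.975^k: k = 6 gives 0.141; k = 18 gives 0.366.

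**Common correlation ρ.** Write each test statistic as √ρ·U + √(1−ρ)·E, with U shared and all terms standard normal, and c = 1.96.
- Either direction: 1 − ∫φ(u)[Φ((c − √ρu)/√(1−ρ)) − Φ((−c − √ρu)/√(1−ρ))]^k du
- Improvement only: 1 − ∫φ(u)[Φ((c − √ρu)/√(1−ρ))]^k du

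| k | ρ | Either direction | Improvement only |
|---|---|---|---|
| 1 | – | 5% | 2.5% |
| 6 | 0 | 26.5% | 14.1% |
| 6 | 0.7 | 16.4% | 8.2% |
| 18 | 0 | 60.3% | 36.6% |
| 18 | 0.7 | 27.7% | 13.9% |

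Increasing the correlation to 0.9 still leaves 10.8% (k = 6) and 15.1% (k = 18) in either direction.

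**Significant versus good.** In a paired t-test the smallest mean change reaching p < 0.05, in SDs of the change, is t(0.975, n−1)/√n. This is 2.001/√60 = 0.26 at n = 60 and 1.980/√120 = 0.18 at n = 120. No SD is given, so this cannot be turned into score points.

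**The case against.** The other side has several fair points.

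- **The count is a reading.** A reader might infer that 18 tests are planned. The Statistical analysis section says only functional scores, and the five-score sentence explains how KOOS is scored, not what is tested. The Variables table supports 6. This stands, and it is why the range is given; 6 tests still exceed the nominal level.
- **An any-one-wins rule is not written.** A reader might infer that one significant result out of many confirms the hypothesis. The plan states no such rule. The hypothesis joins clinical and functional results over short and medium term, and if all had to succeed there would be no inflation. The documents support neither rule; the gap is that none is given.
- **The ANOVA could act as an omnibus test per score.** It could, but it is not named as primary or as a gate. Even so used, it would leave up to six unadjusted score-level tests.
- **Two-sided figures count worsening.** A reader might take 60% as the risk of false success. It is not: it assumes independence and includes deterioration. The improvement-only column is the relevant one.
- **The error level is probably a slip.** The nearby 95% confidence interval suggests 5% was meant. That is likely, but it is not stated for these tests, and stating it would leave the multiplicity.
- **Chance is not the main threat.** There is no control arm, and participants also receive coaching and stretching, 72 hours without sport, and ice. A real before-after change could arise without any product effect. This stands in full and is not cured here.

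**Conclusion.** The point holds in this form: several scores at three visits feed one undefined hypothesis, with no primary score or visit, no multiplicity rule and no valid significance level. On either reading of the test count, the chance of at least one false improvement is above the 2.5% of a single test. It is 14.1% to 36.6% under independence and about 8% to 14% at a common correlation of 0.7. In either direction the figures are 26.5% to 60.3% and about 16% to 28%, against 5%.

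These figures rest on an assumed two-sided 5% per test, an assumed correlation and no true change. They measure what the plan leaves open; they do not show that a chance result will be claimed. The defect concerns which claims the analysis can support and can be repaired in wording.

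**What to change.** 1. Replace the standard-error phrase with a two-sided significance level of 5%.
2. Name one primary score at one visit that fits the objective, for example one KOOS score or IKDC at 6 months. The choice is the sponsor's. Say whether KOOS is analysed as one score or five.
3. Test it as a paired change from baseline, or as a baseline-to-visit contrast in a repeated-measures model, and state the role of the ANOVA.
4. Test any second score in fixed sequence, only if the primary is significant. Report the rest as estimates with 95% confidence intervals, or with Holm adjustment.
5. State the null as zero mean change on the primary score, and the conclusion as changed from baseline rather than good. This corrects the label only: a small change can still be significant, and a claim of good results would need a threshold that the plan does not give.
6. Record whether outcome data had been seen. The protocol is dated 01/12/2023 and its population window is June to October 2022, so on either reading of the date some follow-up data would exist if the schedule held. If results have been seen, label the choice post hoc or adjust all tests.

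**Cost.** No new data or visits. Isolated significant results on other scores or visits would no longer be confirmatory. Naming one test also keeps sensitivity. With 80% power and n = 60 (normal approximation), the detectable mean change is (1.960 + 0.842)/√60 = 0.36 SD of change. Keeping all 18 confirmatory at 0.05/18 = 0.0028 would need (2.991 + 0.842)/√60 = 0.49 SD. The report should still say that a before-after change is not evidence of the product's own effect.

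### The only rank test named for a before-versus-after comparison in one cohort is an independent-samples test, and the stated error level is not a significance level

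*Combined protocol and SAP*

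**What the plan says.** The first Study Design heading, under Methods, describes a single cohort: "This research will be a cohort study, prospective and unidirectional direction". The Specific Objectives set the comparison: "To compare the clinical and functional results of patients with sport-associated knee pain after before and after treatment". The later Study Design section has KOOS and IKDC recorded before the injections and again at 15 days, 3 months and 6 months, in the same people.

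The Statistical analysis section then says:

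- on timing: "Recorded data of the functional scores will be evaluated before and after treatment, also at 15 days, 3 and 6 months";
- on tests and error level: "t-test for parametric and Wilcoxon Mann Whitney for non-parametric variables, a standard error of 95% is allowed";
- on change over visits: "Differences in time will be calculated and group compared by Anova test".

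A 95% confidence level appears once, for correlation, relative risk, attributable risk and Fisher's test: "will be made with a confidence interval of 95"%. No significance level or sidedness is stated for the score comparisons. No sentence calls any test paired, signed-rank or repeated-measures.

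**The concern.** The main data are repeated scores on the same participants. Mann-Whitney (also called the Wilcoxon rank-sum test) assumes two independent samples. If the scores are not treated as normal and the text is followed literally, the before-versus-after comparison is made with a test that ignores the pairing. When a person's scores at two visits are positively correlated, such a test overstates the variability of the change. P-values come out too large, and small real changes can be missed.

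The t-test and ANOVA raise a lesser problem. Each has an independent-samples and a within-person form, and the plan does not say which is meant. Two analysts could follow the same text and report different p-values and intervals for the main efficacy comparison. The error statement does not help them, because a standard error is not a probability of false rejection and 95% cannot be the level intended.

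**Working it through.** **What can be reproduced.** The plan reports no figure on this point. The Sample Size section gives limits of 60 and 120 participants beside a formula with no values entered, so that range cannot be re-derived. The point does not depend on it, and 60 and 120 are used here only as sample sizes.

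**Assumptions, none from the documents.** One score per participant per visit; normal scores with equal SD at both visits; within-person correlation r of 0.3, 0.5 or 0.7; two-sided 5% test; true change of 0, 0.3, 0.6 or 0.8 SD of the score.

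**Step 1: standard errors of the mean change, in SD units.** Unpaired: √(2/n). Paired: √(2(1−r)/n). Their ratio is 1/√(1−r), which is 1.20, 1.41 and 1.83 for r = 0.3, 0.5 and 0.7. At n = 60 the unpaired value is √(2/60) = 0.183. The paired values are 0.153, 0.129 and 0.100. The corresponding 95% intervals are 0.72 SD wide unpaired, against 0.61, 0.52 and 0.40 SD paired. This applies only if the t-test is also run unpaired.

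**Step 2: formula check of type I error.** An unpaired t-test on paired data rejects a true null with probability 2[1 − Φ(1.96/√(1−r))]. At r = 0.5 this is 2[1 − Φ(2.77)] = 0.56%. At r = 0.3 and 0.7 it is 1.9% and 0.03%. The rank test should behave similarly.

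**Step 3: rank tests by simulation, n = 60** (200,000 trials per cell for type I error of Mann-Whitney, 20,000 for power).

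| | r = 0.3 | r = 0.5 | r = 0.7 |
|---|---|---|---|
| Mann-Whitney, true type I error | 2.1% | 0.7% | 0.08% |
| Mann-Whitney, power at 0.3 SD | 33% | 31% | 27% |
| Signed-rank, power at 0.3 SD | 47% | 61% | 82% |
| Mann-Whitney, power at 0.6 SD | 92% | 95% | 98% |
| Signed-rank, power at 0.6 SD | 96% | 99.5% | 100% |

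The signed-rank test keeps its level (4.7% to 5.1%). At r = 0 the two tests perform alike (about 5% type I error, 35% power at 0.3 SD). At 0.8 SD both have about 99% power or more.

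**Step 4: n = 120.** At 0.3 SD, Mann-Whitney has 64%, 66% and 70% power, against 77%, 89% and 98% for signed-rank. At 0.6 SD both are at least 99%.

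**Step 5: if correlation fades with time.** Taking 0.7, 0.8 or 0.9 per month, the baseline-to-6-month correlation is 0.7⁶ = 0.12, 0.8⁶ = 0.26 or 0.9⁶ = 0.53. At 0.3 SD and n = 60, signed-rank power is then about 39%, 45% and 63%, against 35%, 33% and 30%. The 6-month loss could therefore be well below the r = 0.7 column.

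**Step 6: ANOVA over four visits.** Under the same fading correlations, an uncorrected repeated-measures ANOVA at n = 60 rejects a true null 6.7%, 7.1% and 7.7% of the time. With the Greenhouse-Geisser correction the rates are 4.6%, 4.8% and 4.9%. Adding only the words repeated measures would therefore not be enough.

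**The case against.** The strongest reply is that the plan is loosely worded and the intention is sound. Most of its parts have force.

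- The sentence on ANOVA opens with differences in time, which points to a within-person analysis. This stands, and it is why the t-test and ANOVA are treated as unspecified only.
- The rank-test phrase may be two tests run together, Wilcoxon signed-rank and Mann-Whitney. That is possible, but the text does not say so, and the combined name normally denotes the independent-samples test.
- Mann-Whitney has a legitimate use here: the variables table lists gender, BMI class and athlete level, and associations are planned. This stands, but it leaves the before-versus-after scores with no rank test.
- The 95% confidence level elsewhere suggests that 5% was meant. Probably so; that part is a wording correction.
- The error is conservative and nearly disappears for large changes, and nothing in the documents places the trial in the small-change region. This stands and limits the severity.

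Two stronger readings are tempting. First, a reader might infer from the headings "Before treatment Group" and "After treatment Group" that the plan treats the two time points as independent groups throughout. Those headings introduce lists of procedures. They do not define analysis samples, so the inference fails.

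Second, because both knees can be injected and the data sheet in Appendix 3 allows both sides as affected, a reader might infer that knees will be analysed as separate observations and produce false positives. No section plans this. The IKDC and KOOS forms ask about one knee and have no side field, the data sheet carries one participant ID, and the sample size counts participants. How to handle participants with both knees affected is a separate question.

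**Conclusion.** The concern holds in a limited form. As written, the named rank test is wrong for the main comparison and the stated error level is not a significance level. The t-test and ANOVA lack a needed specification but are not wrong. Severity is low to moderate.

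The consequence falls on small effects. At 60 participants and a 0.3 SD change, following the text literally would cost roughly 14 to 55 percentage points of power over r = 0.3 to 0.7 (47 − 33 and 82 − 27). At 0.6 SD the loss is about 4 points or less. With one score per participant and positive correlation, the literal test would not inflate false positives. These sizes rest entirely on the assumed correlations and shifts, since the documents give no SD, correlation or expected effect. The mismatch between test and design does not depend on them.

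**What to change.** Replace the sentences on the t-test, rank test, error level and ANOVA with:

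> Change from baseline in KOOS and IKDC at 15 days, 3 months and 6 months is tested within participant with the paired t-test, or the Wilcoxon signed-rank test for non-normal differences, with 95% confidence intervals. Change over the four visits is tested by repeated-measures ANOVA with Greenhouse-Geisser correction. Mann-Whitney is used only for comparisons between different participants. The two-sided significance level is 5%.

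The plan should also say how non-normality is judged and list the between-participant comparisons. A mixed model for the four visits is an acceptable alternative; one method should be named. Because the elimination criteria remove participants with incomplete follow-up, the corrected ANOVA is workable as the plan stands. Multiplicity over two scores and three visits is not settled by this wording and needs its own sentence.

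The cost is wording and a little more analysis work, with no new data. Timing matters: the Research Universe section gives June to October 2022, so six-month follow-up would end about April 2023. The document date, 01/12/2023, can be read as 12 January or 1 December 2023. If data were already collected when the change is made, it must be dated and reported as a late amendment.
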